## 7.2.3 Definition of an Unexpected Adverse Event

An unexpected adverse drug event is any AE, the specificity or severity of which is not consistent with information in the current IB for an unapproved investigational product.

**Suspected Unexpected Serious Adverse Reaction (SUSAR)** is a SAE assessed as unexpected by the Sponsor and that is judged by either the reporting PI or the Sponsor to have a reasonable causal relationship to the investigational product.

The sponsor will report all suspected unexpected serious adverse reactions, in compliance with regulatory guidelines and the Code of Federal Regulations, Title 21, Volume 5, revised as of April 1, 2018, 21 CFR 312.32 - IND safety reporting

#### 7.2.4 Exceptions in the Reporting of SAE

There will be no exceptions in the reporting of SAEs in this study, as this is a first-in-man study.

agalin A subsidiary of Bio	nnune DLINERX	PRIVILEGED & CONFIDENTIAL
Investigational Product: AGI-134		Protocol No. AGI-134.FIM.101
Phase: I/IIa	l l	Version 6.1 31 May 2021

## 7.2.5 Notification of SAE

#### 7.2.5.1 Initial Notification of SAEs

An initial SAE Report Form must be completed and sent by fax/email to the Sponsor's MM within 24 hours of the PI's knowledge of the event. Any fatal or life-threatening event should be reported immediately, by phone, fax or email. Reporting SAEs to regulatory authorities and/or IRBs/IECs must comply with local regulations.

The initial SAE report will be followed within 24 hours by a completed SAE report including a sufficiently detailed narrative to allow for a medical assessment of the case, as well as copies of hospital case reports, results of applicable diagnostic tests, laboratory results, biopsy results, autopsy reports and other documents when requested and applicable.

## Minimum Criteria for a Valid Initial SAE Case:

For regulatory purposes, initial SAE reports should be submitted to the Sponsor's MM or designee immediately and should include:

- 1. A suspected investigational product (whether or not it is suspected to be related investigational product)
- 2. An identifiable subject (i.e., study subject number)
- 3. An AE with the PI's assessment of seriousness
- 4. An identifiable reporting source (PI contact details)

Once sent, the SAE form and accompanying documentation should be placed in the SAE section of the Investigator's site file.

SAEs will be reported to the IRB/IEC and regulatory authorities as required by local regulations and International Conference on Harmonisation good clinical practice (ICH GCP) guidelines.

## 7.2.5.2 Follow-up of SAEs

Follow-up of all SAEs that occur during the study will continue until their satisfactory resolution or stabilisation. In outstanding cases, an SAE may be defined as "ongoing without further follow-up" if mutually agreed by the PI and Sponsor.

Protocol AGI-134.FIM.101 CONFIDENTIAL Page 70 of 108

agalimmune A subsidiary of BIOLINERX		PRIVILEGED & CONFIDENTIAL
Investigational Product: AGI-134	A Phase I/IIa, multicentre, two-parts, open label study designed to evaluate the safety and tolerability of escalating	Protocol No. AGI-134.FIM.101
Phase: I/IIa		Version 6.1 31 May 2021

A Follow-up SAE Report Form must be completed by the site (marked as "Follow-up report") and sent to the Sponsor's MM within a reasonable timeframe (an SAE Follow-up report is required whether or not there is any additional information to the initial report).

The contact information for Follow-up SAE reporting is the same as for initial SAE reports (see above section).

As for the initial SAE report, once sent, the Follow-up SAE report and accompanying documentation should be placed in the SAE section of the Investigator's Site File.

## 7.2.6 Reporting of Pregnancy and Lactation to the Sponsor

Although pregnancy and lactation are not considered AEs, it is the responsibility of PIs or their designees to report any pregnancy or lactation in a subject or subjects' partner (spontaneously reported to them) that occurs during the study.

Pregnancies and lactations that occur after the ICF is signed but before Baseline must be reported by the PI and the subject should be excluded from the study.

Pregnancies and lactations that occur from the time of ICF signature through 120 days following Termination/ET visit, or 30 days following Termination/ET visit if the subject initiates new anticancer therapy, whichever is earlier, must be reported by the PI and captured in the eCRF. All reported pregnancies must be followed to the completion/termination of the pregnancy. Pregnancy outcomes of spontaneous abortion missed abortion, benign hydatidiform mole, blighted ovum, foetal death, intrauterine death, miscarriage and stillbirth must be reported as serious events (under Important Medical Event). If the pregnancy continues to term, the outcome (health of infant) must also be reported.

Such events must be reported to the Sponsor within 24 hours of the PI's knowledge of the event by fax or by email.

Email:	
Fax:	

agalin A subsidiary of Bio	PRIVILEGED & CONFIDENTIAL
Investigational Product: AGI-134	Protocol No. AGI-134.FIM.101
Phase: I/IIa	Version 6.1 31 May 2021

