- 13. Women of childbearing potential and all men must agree to use 2 methods of an adequate contraception: One barrier method (e.g. diaphragm, or condom or sponge, each of which are to be combined with a spermicide) and one hormonal method (e.g. oral, transdermal patch, implanted contraceptives or intrauterine device) prior to study entry and for the duration of study participation through 120 days after the last dose of study treatment. Subjects that are highly unlikely to conceive (e.g. surgically sterile, postmenopausal, or not heterosexually active) are exempt. Confirmation that female subjects are not pregnant must be established by a negative serum β-human chorionic gonadotropin (βhCG) pregnancy test result obtained during Screening. Pregnancy testing is not required for postmenopausal or surgically sterilised women.

Non-childbearing potential is defined as (by other than medical reasons):

• ≥45 years of age and has not had menses for over 2 years.

agalin A subsidiary of Bio	nnune DLINERX	PRIVILEGED & CONFIDENTIAL
Investigational Product: AGI-134		Protocol No. AGI-134.FIM.101
Phase: I/IIa		Version 6.1 31 May 2021

 <45 years of age and amenorrhoeic for > 2 years without a hysterectomy and oophorectomy and a Follicle Stimulating Hormone (FSH) value in the postmenopausal range upon pre-trial (screening) evaluation.

For women, post hysterectomy, bilateral oophorectomy, bilateral salpingectomy or bilateral tubal ligation and vasectomy for men at least 6 weeks prior to screening. Documented hysterectomy or oophorectomy must be confirmed with medical records of the actual procedure or confirmed by ultrasound. Tubal ligation must be confirmed with medical records of the actual procedure.

- 14. Subject is able and willing to comply with the requirements of the protocol.
- 15. Subject is able to voluntarily provide written informed consent.

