- 16. Has received other experimental therapies or used an investigational device within 28 days of the first dose of treatment
- 17. Has had prior chemotherapy, targeted small molecule therapy, or radiation therapy within 14 days before first AGI-134 administration or has not recovered from treatment related AE> Grade 19
- 18. Has had a prior anti-cancer monoclonal antibody (mAb) within 28 days before first AGI-134 administration or who has not recovered from AE > Grade 1.
- 19. Is pregnant or breastfeeding or expecting to conceive or father children within the projected duration of the study, starting with the Screening visit through 120 days after the last dose of study treatment. Women with a positive pregnancy test within 72 hours from Baseline.
- 20. Has unstable angina, new onset angina within the last 3 months, myocardial infarction within the last 6 months, uncontrolled atrial fibrillation, or current congestive heart failure with New York Heart Association Class III or higher.
- 21. Has a known current additional malignancy that is progressing or requires active treatment. Exceptions are non-melanoma skin lesions, adequately treated basal cell or squamous cell carcinoma that has undergone potentially curative therapy or carcinoma in situ of the cervix.
- 22.  $O_2$  saturation < 92% (on room air).
- 23. Has an underlying medical condition that would preclude study participation or other psychological, social or physical examination (PE) finding or a laboratory abnormality that the PI considers would make the subject a poor study candidate or could interfere with protocol compliance or the interpretation of study results.
- 24. Has known psychiatric or substance abuse disorders that would interfere with cooperation with the requirements of the study.

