## 5.4 Termination or Early Termination Study Visit (Week 54 or ET)

The total study participation period is 54 weeks. Treatment with AGI-134 will be provided for up to 4 cycles (12 weeks). A Termination visit will be performed at Week 54 for all subjects.

In case of Early Termination (ET), all reasons for treatment discontinuation will be documented in the source documents yet only one reason (the most severe) for ET should be recorded in the eCRF. If one of the reasons for early termination is an AE, this should be chosen as the reason. Every effort should be made to follow-up these subjects until resolution or stabilisation of the AE.

At this visit, the following activities will be performed. Exceptions for assessments may be provided in case these assessments were done 1-2 cycles prior to Termination visit and after discussion and approval by the study MM.

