## 6.7.3 Contraception

AGI-134 effect on foetus in utero was not tested to date.

For this study, male subjects will be of non-reproductive potential, if they have azoospermia (whether due to having had a vasectomy or due to an underlying medical condition).

Males and non-pregnant, non-breastfeeding females may only be enrolled if they are willing to use 2 methods of birth control or are considered highly unlikely to conceive. Highly unlikely to conceive is defined as;

- 1) surgically sterilised
- 2) Women of non-childbearing potential (see definition in section 4.1 Inclusion Criteria)
- 3) not heterosexually active for the duration of the study when this is in line with the preferred and usual lifestyle of the subject.

The two birth control methods can be a barrier method plus a hormonal method to prevent pregnancy. Subjects should start using birth control from Screening visit (or 21 days prior to investigational product administration for oral contraception) and throughout the Core Study up to 120 days after the last dose of study medication.

The following are considered adequate barrier methods of contraception: Diaphragm, condom (by the partner) or sponge; each of which are to be combined with a spermicide or a copper intrauterine device as per local regulations or guidelines. Appropriate hormonal contraceptives will include any registered and marketed contraceptive agent that contains an oestrogenic and/or a progestational agent (including oral, subcutaneous, intrauterine or intramuscular agents).

Subjects should be informed that taking the study medication may involve unknown risks to the foetus (unborn baby) if pregnancy were to occur during the study. In order to participate in the study, subjects of childbearing potential must adhere to the contraception requirement (described above) for the duration of the study and 120 days after the last dose of study treatment. If there is any question that a subject of childbearing potential will not reliably comply with the requirements for contraception, that subject should not be entered into the study.

20		PRIVILEGED & CONFIDENTIAL
Investigational Product: AGI-134	A Phase I/IIa, multicentre, two-parts, open label study designed to evaluate the safety and tolerability of escalating	Protocol No. AGI-134.FIM.101
Phase: I/IIa		Version 6.1 31 May 2021

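### Mandatory pregnancy reporting can close up to 90 days before the protocol's 120-day post-dose conception-avoidance period ends, for subjects who leave early and start new anticancer therapy.

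*Combined protocol and SAP*

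**What the plan says.** **Reporting window (Section 7.2.6).** The default window is "Pregnancies and lactations that occur from the time of ICF signature through 120 days following Termination/ET visit". The same sentence then gives a second limit: "or 30 days following Termination/ET visit if the subject initiates new anticancer therapy, whichever is earlier, must be reported by the PI". Both limits count from the Termination/ET visit. The sentence also requires eCRF capture.

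**Conception-avoidance window.** Three places count from the last dose and make no exception for new anticancer therapy:
- Inclusion criterion 13 (Section 4.1): contraception "for the duration of study participation through 120 days after the last dose of study treatment".
- Exclusion criterion 19 (Section 4.2): no expectation of conceiving or fathering a child, "starting with the Screening visit through 120 days after the last dose of study treatment".
- Section 6.7.3: birth control "throughout the Core Study up to 120 days after the last dose of study medication".

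Section 6.7.3 gives the context: "AGI-134 effect on foetus in utero was not tested to date".

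**Timing of the two anchors (Section 5.4).** On dosing: "Treatment with AGI-134 will be provided for up to 4 cycles (12 weeks"). On the visit: "A Termination visit will be performed at Week 54 for all subjects". Section 4.6 asks for the Early Termination procedures in everyone who withdraws prematurely. Neither section sets a minimum time between the last dose and that visit.

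**The concern.** The protocol sets 120 days after the last dose as the period in which subjects must avoid conception. One would expect it to collect pregnancies over at least that period. Because Section 7.2.6 uses a different anchor and shortens the window when new therapy starts, cover is shortest for the subjects dosed most recently. A Week 54 completer, last dosed around Week 10, is covered for most of a year after dosing. A subject who stops at progression shortly after a dose and moves to other treatment can pass out of the explicit window within weeks.

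That path is foreseeable. Section 4.5 lists progression as a reason to stop. Section 5.12 places the first post-baseline tumour assessment at Week 9, before the Cycle 4 dose. Section 6.7.2 allows other treatments after progression. AGI-134 has not been given to humans before and foetal effects are untested, so any exposed pregnancy is scarce safety information that cannot be recovered later if nobody records it.

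**Working it through.** The plan gives no figure of its own to reproduce; the check is date arithmetic.

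**Inputs**
- Reporting closes at ET + 120 days, or ET + 30 days if new therapy starts, whichever is earlier (Section 7.2.6).
- Conception avoidance ends 120 days after the last dose (Sections 4.1, 4.2, 6.7.3). Some of this text also mentions the duration of the study; 120 days post-dose is taken as the minimum.
- x = days from last dose to the Termination/ET visit. Assumption: x can be any value from 0 upward, since no minimum is stated.

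**Formulas, in days after the last dose**
- With new therapy, reporting closes at x + 30, so gap = max(0, 120 − (x + 30)) = max(0, 90 − x).
- Without new therapy, reporting closes at x + 120, so gap = max(0, 120 − (x + 120)) = 0 for every x.

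**Results with new therapy**

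| x (days) | Reporting closes (x + 30) | Gap (90 − x) | Share of 120 days |
|---|---|---|---|
| 0 | 30 | 90 | 75% |
| 14 | 44 | 76 | 63% |
| 21 (one cycle) | 51 | 69 | 57.5% |
| 30 | 60 | 60 | 50% |
| 56 (Week 18 visit after a Week 10 dose: (18 − 10) × 7) | 86 | 34 | 28% |
| 60 | 90 | 30 | 25% |
| 90 or more | 120 or more | 0 | 0% |

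**Week 54 completer.** x = (54 − 10) × 7 = 308. Reporting closes 338 days after the last dose with the cut and 428 without it. No gap.

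**Worked case.** Third dose on Day 43, progression on the Week 9 scan, ET on Day 64, then new therapy. Reporting closes on Day 64 + 30 = 94. The 120-day period ends on Day 43 + 120 = 163. Gap = 163 − 94 = 69 days. The first long-term follow-up call (Section 5.5: 9 weeks ± 7 days after ET) falls on Day 64 + 63 = 127 (Days 120 to 134), after reporting has closed and while the 120-day period is still running. Pregnancy is not among the topics listed for that call.

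**A further ambiguity.** Section 7.2.6 does not say by when new therapy must start for the 30-day limit to apply. Read literally, therapy begun 60 days after ET would close the window retrospectively at day 30.

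**The case against.** The best opposing case is that other provisions already cover these pregnancies.
- The opening sentence of Section 7.2.6 makes the investigator report any pregnancy in a subject or partner that is volunteered during the study, with no cut-off for new therapy. Long-term follow-up runs for 5 years and includes subjects who left early, so a pregnancy mentioned on a call could be reportable. Section 7.2.6 requires every reported pregnancy to be followed to its end.
- The partner sentence in Section 6.7.3.1 states no end date of its own.
- A congenital anomaly is an SAE (Section 7.2), and SAEs judged related stay reportable for up to 5 years after Termination/ET (Section 7.2.2).
- A serum pregnancy test is done at Termination/ET (Section 5.4).

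A reader might therefore go too far the other way and infer from the 30-day limit that a pregnancy in the gap need not be reported or followed at all. These provisions do not support that.

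They do not close the gap either. The opening sentence is passive, gives no end date, and is followed by an explicit window for mandatory reporting and eCRF capture; which governs is unclear. The partner sentence refers back to Section 7.2.6. The SAE route needs a serious event, a causality judgement and someone to bring it forward. The ET test cannot detect later conceptions.

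Three further objections carry weight. No text says the two windows must match. Stopping collection at new therapy resembles the AE and SAE rule, though that rule counts from the last dose. And the numbers are small: at most about 24 + 35 = 59 subjects, with conception needed despite two required contraceptive methods. Repeating a scan to confirm progression (Section 5.12) can delay ET, but treatment may continue meanwhile, and a further dose resets x.

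**Conclusion.** The inconsistency is real and its size is 90 − x days. It applies only when the ET visit comes less than 90 days after the last dose and the subject starts new anticancer therapy. Ninety days is the limit, reached only if ET falls on the dosing day; 69 days at x = 21 and 34 days at x = 56 are illustrations, not expected values.

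A reader might infer that most subjects would meet this gap, since new treatment after progression seems likely. The documents permit that course but give no rate of early termination, new therapy or childbearing potential, so frequency cannot be estimated. The supported conclusion is that active reporting and eCRF capture are not assured for part of the protocol's own 120-day period, with partial and ambiguous cover elsewhere. The point is of modest weight, worth correcting because the correction is small. It rests on reading the explicit window in Section 7.2.6 as the operative one and on no minimum dose-to-ET interval.

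**What to change.** - Amend Section 7.2.6 so that pregnancies and lactation in subjects and partners are reported and captured in the eCRF from ICF signature through at least 120 days after the last AGI-134 dose, whether or not new anticancer therapy has started. Keep the present Termination/ET-based limit where it is longer. The gap is then 0 for every x.
- Reconcile this sentence with the opening sentence of Section 7.2.6 and with the partner sentence in Section 6.7.3.1, so that one end date governs.
- Add a pregnancy question to the existing 9-weekly calls in Section 5.5 that cover the period. The second call is nominally x + 126 days after the last dose, so the first two calls normally reach past day 120.

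This changes data collection only, not dosing or the contraception rule. The cost is a protocol amendment with its IRB/IEC submission (Section 9.9) and one question on calls already planned. Following a pregnancy outcome still needs permission, as Section 6.7.3.1 recognises. Some reported pregnancies will also have been exposed to the next therapy, which can be noted on the form.

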### 8 STATISTICAL METHODOLOGY

# 8.1 Sample Size Consideration

As this is a Phase I/IIa study, the exact number of subjects enrolled will depend on the toxicity observed in each dose group and the number of dose groups required to reach MTD. If all four dose groups are required and if each dose group is expanded to 6 subjects (see Safety Assessment Section 8.3), then a total of 24 subjects will be enrolled into Part 1, the dose escalation, of the study. Part 2 is aiming to recruit approximately 35 subjects receiving at least one dose of AGI-134.

# **Analysis Sets**

- Intention-To-Treat (ITT) analysis set: All enrolled subjects who received at least one
  dose of study drug.
- Per-Protocol (PP) analysis set: All enrolled subjects who completed the study according to the protocol without major protocol violations.
- Modified-Intention-To-Treat (mITT) analysis set: All enrolled subjects who receive at least one dose of investigational product and had post Baseline imaging assessment.
- Safety Population: All enrolled subjects who received at least one dose of study drug.

### 8.2 Statistical Methods

This section briefly describes the statistical methods to be used to analyse the data from the study. A detailed Statistical Analysis Plan (SAP) will present the methods in detail. If the methods of the SAP differ from the methods in this section, the methods of the SAP will prevail.

All measured variables and derived parameters will be listed individually and, if appropriate, summarised using descriptive statistics.

For categorical variables, summary tables will be provided giving sample size, absolute and relative frequency, and 95% confidence interval (CI) for proportions.

For continuous variables, summary tables will be provided giving sample size, arithmetic mean, standard deviation, median, minimum and maximum, appropriate percentiles, and 95% CIs for means.

Statistical test performed will be considered statistically significant if the P-value is less than

The data will be analysed using the SAS ® version

The data will be analysed as described in the SAP.

Analysis will be performed for all subjects in the study, as well as for the pre-defined populations, as follows:

- 1. All patients in Part 1
- 2. All patients in Part 1 and 2

Protocol AGI-134.FIM.101 CONFIDENTIAL Page 72 of 108

agalin A subsidiary of BIO		PRIVILEGED & CONFIDENTIAL
Investigational Product: AGI-134	designed to evaluate the safety and tolerability of escalating	Protocol No. AGI-134.FIM.101
Phase: I/IIa		Version 6.1 31 May 2021

- 3. Part 2 patients from a specific sub-population with histologically confirmed advanced cutaneous metastatic melanoma who:
  - 1. Had only one previous treatment with CIP:
    - a) Anti-PD-1 approved for melanoma, and/or
    - b) Anti-cytotoxic T-lymphocyte-associated protein 4 (CTLA-4) therapy approved for melanoma, and
  - 2. Have remained on prior CPI treatment for at least 4 months or have stopped treatment earlier than that, due to toxicity rather than disease progression.

